- 1. Access to the mobile seat interface pressure mapping system (IPM) as a visual feedback system.** This mobile IPM system was designed to provide visual information about seat interface pressure distribution to compensate for lack of sensation on the sitting surface. This variable will be toggled on and off between the A and B phases of the study. The participants will have access to the visual feedback while learning how to complete weight shift maneuvers at the initial visit and then again at home during the A phases (weeks 2 and 4). During the B phases (weeks 1 and 3), they will not have access to the visual feedback from the pressure map. The pressure mapping system consists of a commercially available pressure mat by Vista Medical, and a mobile web-application developed by the research team through a CoDE award provided by the Center for Innovation in 2012 to display the pressure map information on a smartphone screen. The pressure mat connects to the smartphone via Wifi. The smartphone accesses the web application via the phone's data plan while connected to

the mat to display the pressure readings to the user on the phone. No information about the individual, except for the research participant ID number is transmitted to the web application. Each research participant will have a unique password associated with their own ID to use when they log into the web application. The web application resides on a Mayo Clinic server.

2. Education about pressure ulcer risk and how to perform weight shift movements.

Structured education for performance weight shift maneuvers and pressure ulcer prevention will occur during the initial visit. The education method used aligns with principles of the social cognitive theory to facilitate learning. The purpose in providing the education is to ensure all of the participants receive uniform instruction in how to perform weight shifts and to facilitate understanding of the importance of completing them as a protective measure against pressure ulcer development. Because each participant will come into the study at varying levels of understanding about pressure ulcer risk and knowledge of how to complete weight shift maneuvers, the education component is critical to ensure all participants are provided with the same information in the same way.

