2. **Self-efficacy for performing weight shifts.** The second dependent variable, self-efficacy, is measured with a series of four individual questions about self-efficacy for weight shifts for pressure ulcer prevention (Appendix A). Each question is answered by choosing a number from 0-100 to indicate confidence level. This assessment includes an initial question that targets an individual's outcome belief about whether they believe that completing weight shifts will prevent pressure ulcers. This is followed by three questions about their own judgement of their immediate capability to complete weight shift maneuvers based on three criteria: effectiveness (moving enough to impact pressure distribution), consistency (completing weight shifts every half hour), and duration (holding weight shifts for two minutes). The items were written following principles outlined in Albert Bandura's guide to developing self-efficacy assessments (A. Bandura, 2006).

The score for each of the four items will allow preliminary analysis of any change in self-efficacy for specific components of performing weight shifts with the outcome of pressure ulcer prevention. The self-efficacy questions (SE) will be administered in person or by phone a total of 7 times: at start of initial session before any education, at end of session when education is completed, on day 2 when participant has been home for 1 day but no other intervention has been provided (test-retest), and at the end of each of the four phases. The self-efficacy survey will be given twice during the initial visit, 4 times over the phone when participant is called each week, and 1 time during the last visit for a total of 7 times.

Additional demographic information will be obtained from existing medical records and will include date of onset of spinal cord injury, date of birth, history of pressure ulcers on sitting surface, history of pressure ulcer repair surgery, level of spinal cord injury and severity of injury.

Resources: *Describe the available resources to conduct the research (personnel, time, facilities, mentor commitment, etc.):*

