This research project will be conducted by the Primary Investigator ([name]) and her co-Primary Investigator, [name] as part of their NIH R21 award. There is sufficient FTE allocated to each for completion of the work. The subjects will be seen in a clinical exam space within Physical Medicine & Rehabilitation, on Mayo 14, where the Seating and Mobility Clinic practice is.

- (1a) This is a multisite study involving Mayo Clinic and non Mayo Clinic sites. *When checked, describe in detail the research procedures or activities that will be conducted by Mayo Clinic study staff.*
- (1b) Mayo Clinic study staff will be engaged in research activity at a non Mayo Clinic site. *When checked, provide a detailed description of the activity that will be conducted by Mayo Clinic study staff.*

Subject Information

Target accrual is the proposed total number of subjects to be included in this study at Mayo Clinic. A "Subject" may include medical records, images, or specimens generated at Mayo Clinic and/or received from external sources.

Target accrual: 30

Subject population (children, adults, groups): Participants with an existing spinal cord injury who use a wheelchair as their primary means of mobility will be invited to participate in this study.

Inclusion criteria. Participants will meet inclusion criteria if they live in the community, are aged 18 or older, male or female, have paraplegia or quadriplegia due to a spinal cord injury that includes sensory loss below their level of injury, and require full-time wheelchair use for mobility. Participants must demonstrate ability to independently access a smartphone and the required pressure mapping application on the smartphone. The participants must be able to tolerate sitting for a minimum of 6 hours per day, 7 days per week, and they must be able to perform weight shifts independently. They also must be able and willing to attend in-person visits at start and end of the study, about 4 weeks apart. No exclusions related to gender or minority mix identified.

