Weight shifts will be counted as described earlier based on offset angles. The average number of weight shifts for each type of weight shift will be documented by phases A1, B2, A2, B2. The analyses to test the primary hypothesis that overall trunk movement (vector magnitude) and weight shifts will increase in frequency with the use of the mobile pressuring mapping system will be tested using Linear Mixed Effects Regression. When appropriate, post-hoc tests will be performed to test main effects. If a phase x session interaction is present, post hoc tests to analyze and interpret the interaction will be used. Significance is set at $\alpha=0.05$.

Self-efficacy scores will be analyzed by comparing scores SE #1 vs #2, #2 vs #3 (test-retest), and #4 vs #5 vs #6 vs #7 to determine effect of education and use of mobile IPM on self-efficacy. The analyses to test the secondary hypothesis that the scores for the self-efficacy items will increase after education and will increase again with the use of the mobile pressuring mapping system will be tested using Linear Mixed Effects Regression. When appropriate, post-hoc tests will be performed to test main effects. If a phase x session interaction is present, post hoc tests to analyze and interpret the interaction will be used. Significance is set at $\alpha=0.05$.

The results will help determine if there is a cause/effect relationship between use of the pressure map and any increase in weight shifts if that is detected and if results are significant, we can conclude that use of the map resulted in increased movement. We can't conclude that there will be a reduction in

pressure ulcers but we can say that weight shifts, a factor known to contribute to reduced pressure ulcer risk, increases when a wheelchair user has access to a compensatory assistive device to accommodate reduced sensation. The same is true for results of the self-efficacy assessments. We would expect the mean score to improve at each subsequent time-point.

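### The final self-efficacy rating is taken in person and the other three phase ratings by phone, so interview mode is partly mixed into the planned estimate of the map effect

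*Combined protocol and SAP*

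**What the plan says.** All references are to the combined protocol and SAP.

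- **Timing and mode** (Dependent variables, 2. Self-efficacy). Ratings are taken before education (#1), after education (#2), "on day 2 when participant has been home for 1 day but no other intervention has been provided (test-retest" (#3), and "at the end of each of the four phases" (#4 to #7). Two are given at the initial visit, and the rest "4 times over the phone when participant is called each week, and 1 time during the last visit for a total of 7 times".
- **Visits** (Subject Information, inclusion criteria). Participants must "attend in-person visits at start and end of the study, about 4 weeks apart". No other in-person visit is described.
- **Map access** (Independent variables, 1). Participants have the visual feedback "again at home during the A phases (weeks 2 and 4"). For the other weeks: "During the B phases (weeks 1 and 3), they will not have access to the visual feedback from the pressure map".
- **Analysis** (Data Analysis Plan). After #1 versus #2, the comparisons are "2 vs #3 (test-retest), and #4 vs #5 vs #6 vs #7", using linear mixed effects regression at a significance level of 0.05. A phase-by-session interaction is to be followed up if present. No mode term, mode sensitivity analysis or standardisation of mode is stated.
- **Hypothesis 4** has two parts: ratings with the map at home should exceed the rating after education, and should exceed ratings in phases without the map.

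**The concern.** The outcome is a subjective 0–100 confidence rating on items written for this study. Participants know when they have the map, and the research team developed the display application. Answers given face to face may differ from answers given by phone. If they do, part of the difference falls on one side of the map comparison only, and the planned model has no means of removing it. The plan intends to draw cause-and-effect conclusions and extends that intention to self-efficacy, so an avoidable measurement difference between conditions matters even for a secondary aim.

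The pair labelled test-retest has a related weakness. It moves from in person (#2) to phone (#3), so it cannot show repeatability separately from mode.

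**Working it through.** **1. Reproduce the count.** By mode: 2 + 4 + 1 = 7. By time point: 1 + 1 + 1 + 4 = 7. Both match the stated total of seven. With in-person visits only at the start and end, one allocation fits:

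| Rating | When | Map at home | Mode |
|---|---|---|---|
| #1 | before education | no | in person |
| #2 | after education | no | in person |
| #3 | day 2 | no | phone |
| #4 | end of week 1 | no | phone |
| #5 | end of week 2 | yes | phone |
| #6 | end of week 3 | no | phone |
| #7 | end of week 4 | yes | in person |

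**2. Weight of mode in each comparison.** Let m be the in-person-minus-phone shift. The plan gives no formula for a pooled map effect, so equal phase weights are assumed.

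- Map minus no-map, (#5 + #7)/2 − (#4 + #6)/2: (0 + m)/2 − (0 + 0)/2 = m/2.
- #7 − #6: m − 0 = m.
- #5 − #4 and #5 − #6: 0 − 0 = 0.
- Interaction, (#7 − #6) − (#5 − #4): m − 0 = m.
- Map mean minus #2, the other part of Hypothesis 4: m/2 − m = −m/2.

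**3. Can the planned model separate mode?** Read phase as map or no map, and session as first or second pair of weeks. Over #4 to #7 the columns are map (0,1,0,1), session (0,0,1,1), map × session (0,0,0,1) and mode (0,0,0,1). The last two are identical. With the intercept there are five columns of rank 4, so mode can be fitted only if the interaction is dropped.

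**4. Size, as illustration.** The documents give neither m nor an SD, so both are assumed. With independent within-person residuals of SD s, the pooled contrast has variance 4s²/4 = s², hence SD s. With n = 30 (target accrual), a two-sided 0.05 test (sidedness is not stated) and 29 df, the noncentrality is (m/2)/(s/√30). For m = 5 and s = 10 it is 2.5/1.826 = 1.37; for s = 15 it is 2.5/2.739 = 0.91. The chance of a significant result with no true map effect is:

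| m | bias (m/2) | s = 10 | s = 15 | s = 20 |
|---|---|---|---|---|
| 2 | 1 | 0.083 | 0.064 | 0.058 |
| 5 | 2.5 | 0.263 | 0.143 | 0.102 |
| 10 | 5 | 0.754 | 0.423 | 0.263 |

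**5. Effect of moving #7 to phone.** The weight in the map contrast falls from 1/2 to 0, and in the interaction from 1 to 0. Against #2, however, the weight goes from −1/2 to 0 − 1 = −1. Against #3, which is by phone, after education and before home use of the map, it is 0 − 0 = 0.

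**6. If #7 stays in person.** The estimate without it, #5 − (#4 + #6)/2, has mode weight 0. Its variance is s² + s²/2 = 1.5s², so its standard error is √1.5 = 1.22 times that of the four-rating contrast.

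**7. Dependence on phase order.** The Methods section describes an A-B-A-B design, and the vector magnitude text lists A1, B1, A2, B2, which would put A first. The map section places A in weeks 2 and 4. The table in step 1 uses the week numbers, and the day-2 wording is consistent with them. In the reverse order #7 would be a no-map rating, and the weight would be 0 − m/2 = −m/2.

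**The case against.** A reader might infer that any mode effect is credited to the map under Hypothesis 4, or that face-to-face rating inflates the result. The documents do not support either reading.

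- **The confounding is partial.** #5 is a map rating by phone, so #4 versus #5 and #5 versus #6 are clean, and both lie within the planned comparison. This stands.
- **Part of Hypothesis 4 runs the other way.** #2 is in person. If in-person ratings are higher, comparing the map ratings with #2 is biased against the map. This stands.
- **The shift itself is undocumented.** Its size and sign are unknown. Both modes are part of the same study's follow-up, so courtesy could act by phone as well. The larger entries in the table need a 10-point shift, for which the documents give no evidence. This stands, and the percentages are illustrations only.
- **Moving #7 to phone worsens the comparison with #2.** That is so if #2 remains the reference. It does not arise with #3, which is also a rating after education.
- **The interaction test might reveal the problem.** A shift confined to #7 would appear there, but the follow-up could not attribute it to mode.
- **This is a secondary aim, and the item analysis is called preliminary.** True, and the accelerometer outcomes are untouched. That limits the importance of the point without removing the difference in mode.

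**Conclusion.** The point holds as partial confounding of one rating, #7. Any mode shift biases the equally weighted map effect by half its size, and biases #7 versus #6 and the phase-by-session interaction by its full size. The planned model cannot separate it from that interaction. With m = 5 and an assumed SD of 10 to 15, the false-positive rate would be 26% to 14% instead of 5%. The weights follow from the schedule and equal phase weighting; the rates also rest on the assumed m, SD, independence and two-sided test. Direction depends on the sign of m and on the phase order, which the documents must reconcile; reversing the order changes the sign of the bias but does not remove it. This is a cheap improvement to a secondary analysis and does not show that the self-efficacy result would be wrong.

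**What to change.** 1. In the self-efficacy section, state that #7 is collected by phone at the end of week 4, before the final visit, with the same script as #4 to #6.
2. In the Data Analysis Plan, name #3 as the reference for Hypothesis 4's comparison with the post-education rating, because #2 is in person.
3. If #7 stays in person, add a sensitivity analysis of the map effect without #7, accepting a standard error about 22% larger under the assumptions above.
4. Describe #2 versus #3 as a change across mode and one day at home, not as pure test-retest reliability.
5. Reconcile the A-B-A-B label with the stated week numbers.

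The cost is one short call per participant in place of four questions at the last visit, and a few sentences in the protocol.

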Dependent variables. There are two dependent variables in this study: overall trunk movement (vector magnitude and weight shift count) measured through a single tri-axial accelerometer and self-efficacy for performing weight shifts to prevent pressure ulcers measured with four items on a self-efficacy assessment written specifically for this study.

1. Trunk movement. Trunk movement will be measured using a single tri-axial accelerometer attached to the participant's sternum with a chest strap. The accelerometer used in this study is the Actigraph GT3X+ (Culiolo & Shaw, 2016). The GT3X+ measures accelerations within a dynamic range of +/- 6 units of gravity (G) in three planes of trunk motion, the vertical, anteroposterior, and mediolateral. The accelerometer will be worn throughout the study while the individual is in their wheelchair and taken off at night when sleeping. Trunk movement will be reported in two ways: vector magnitude for counting total movements of the trunk and counts of specific weight shift movement magnitudes based on offset angles of the accelerometer measures. Frequency of data collection will be 30Hz. When measuring continuously for 24 hours/day at 30Hz, the published battery life is 22.5 days and memory limit is 42.5 days. This will require that the participants charge the battery midway through the study. A more detailed description of the specific variables follows.

a. Vector magnitude. A total count of trunk movements in the form of vector magnitude will be averaged across each phase for each participant. The Actigraph GT3X+ provides raw values in each of the three axes. A composite vector magnitude of these three axes (VM) in a specific period of time is a "count" of movement. VM is the square root of the sum of each axis squared. VM will be calculated per second of wear time. For each of the 7 days in a phase, there will be a total VM, which will be graphically portrayed by day for visual analysis of trends for movement within each phase. The overall VM for each phase will be the average VM across the 7 days. This average VM per phase (A1, B1, A2, B2) will be used as the dependent variable for overall trunk movement.

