To determine wear time, two approaches will be used. First, the participants will be asked to document time up to chair and out of chair each day on a daily log (Appendix C). Second, raw accelerometer data will be analyzed for a specific change in orientation based on offset angles and lack of accelerations for a time period of 15 minutes. By asking participants to invert the device on the table, and because this position would be difficult for the device to be in while worn on the chest, it allows for easier detection of the non-wear periods. When there is a question about wear time, the daily logs will be compared with the raw data.

b. **Weight shift count.** Trunk angle offsets from upright will be derived from the raw accelerations. When starting from an upright orientation, an offset angle will be measured in both the anteroposterior and in the mediolateral planes. To determine each participant's trunk angles while performing the prescribed weight shifts, the accelerometer will record while each participant performs a specific sequence of the weight shift maneuvers. From the initial recordings, an algorithm will be adapted for each participant to detect weight shifts in the field-collected accelerometer data. Movements reaching the defined threshold for partial and full weight shifts will be counted. A total count per day and an average count per phase will be recorded. The total daily count, when graphed, can be visually analyzed for trends during each phase. The average phase counts can be compared across control versus intervention conditions.

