Subject ID, subject code or any other person-specific unique identifying number, characteristic or code that can link the subject to their medical data	X	
Dates: All elements of dates [month, day, and year] directly related to an individual, their birth date, date of death, date of diagnosis, etc. Note: Recording a year only is not a unique identifier.	X	
Social Security number		
Medical device identifiers and serial numbers		
Biometric identifiers, including finger and voice prints, full face photographic images and any comparable images		
Web Universal Resource Locators (URLs), Internet Protocol (IP) address numbers, email address		
Street address, city, county, precinct, zip code, and their equivalent geocodes		
Phone or fax numbers	X	
Account, member, certificate or professional license numbers, health beneficiary numbers		
Vehicle identifiers and serial numbers, including license plate numbers		

Check 'None' when none of the identifiers listed above will be recorded, maintained, or shared during the conduct of this study. (exempt category 4)	 None	 None
---	-------------------------------	--

Data Analysis

Power analyses and study endpoints are not required for minimal risk research, pilot or feasibility studies.

No statistical information. *If checked, please explain:*

Data Analysis Plan:

Post-processing of the Actigraph data will be completed with custom software in MATLAB (Mathworks, Natick, MA).

The **vector magnitude** for each second of data during wear-times will be classified as a period of activity or inactivity. Additionally, total vector magnitude of movement for each day will be determined by summing the VM of all active wear-times. Then, for each 7-day phase, the daily values will be averaged for a resulting average phase VM. There will be an average phase VM for each phase A1, B1, A2, and B2.

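### Both movement outcomes are averages of daily totals, and no planned analysis adjusts for wear or chair hours or compares them between map and no-map weeks, so unequal hours could pass unseen into the causal conclusion

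*Combined protocol and SAP*

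**What the plan says.** **Vector magnitude.** The Data Analysis Plan states that "total vector magnitude of movement for each day will be determined by summing the VM of all active wear-times". The Dependent variables section, item 1a, adds that "The overall VM for each phase will be the average VM across the 7 days", and makes this phase average the dependent variable. The same item also says that "VM will be calculated per second of wear time".

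**Weight shifts.** Item 1b says: "A total count per day and an average count per phase will be recorded". The phase averages are what is compared between conditions.

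**Exposure.** The wear period is not of fixed length: "The accelerometer will be worn throughout the study while the individual is in their wheelchair and taken off at night when sleeping". It is recorded in two ways. For the log, "the participants will be asked to document time up to chair and out of chair each day on a daily log". Non-wear is also detected from device orientation and 15 minutes without acceleration. The two sources meet only case by case: "When there is a question about wear time, the daily logs will be compared with the raw data".

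**Model and conclusion.** The Data Analysis Plan names linear mixed effects regression at a 0.05 level. It names no wear-time denominator, offset or covariate, and no comparison of wear between phases. It then says that a significant result allows the conclusion that the map increased movement.

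**The concern.** A daily total is the product of how much a person moves per hour and how many hours are observed. Hours in the chair, and hours with the device on while in the chair, can vary from week to week. If they differ systematically between the map weeks (2 and 4) and the no-map weeks (1 and 3), the totals can differ with no change in movement per hour.

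Three explanations of a higher total would then be open: more movement per hour, more hours in the chair, or fewer seated hours with the device off. The plan holds the records needed to tell them apart but schedules no analysis that does so. What is at stake is the meaning of the closing causal statement. A reader would probably take it to mean that people shift their weight more often while seated, and the planned analysis would not establish that.

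The error can also run the other way: fewer recorded hours in map weeks could hide a real gain in hourly movement.

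**Working it through.** **No planned figure to reproduce.** The documents give no power calculation, effect size, SD or wear hours. From the documents: target accrual 30, and a sitting requirement ("The participants must be able to tolerate sitting for a minimum of 6 hours per day, 7 days per week"). All other inputs below are assumptions.

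**Step 1. Is the analysed VM a rate?** Item 1a mentions VM per second of wear, but its next sentences form a daily total and average it over 7 days, and the Data Analysis Plan sums it. The consistent reading is that VM is computed for each second and then summed. Nothing similar is written for weight shifts.

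**Step 2. Mean shift.** Let *B* be base hours, *s* the added hours in map weeks, and *a* the activity of added hours relative to the rest (1 = same, 0 = none). With no change in the underlying rate:
- total changes by *a* × *s* / *B*
- per-hour rate changes by (*B* + *a* × *s*)/(*B* + *s*) − 1

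For *s* = 0.5 h:

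| Base | a | Total | Rate |
|---|---|---|---|
| 10 h | 1 | +5.0% | 0 |
| 10 h | 0.5 | +2.5% | −2.4% |
| 10 h | 0 | 0 | −4.8% |
| 6 h | 1 | +8.3% | 0 |
| 6 h | 0.5 | +4.2% | −3.8% |
| 6 h | 0 | 0 | −7.7% |

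Masking: a true +10% hourly rate with 10% less wear gives 1.10 × 0.90 = 0.99 of the original total.

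**Step 3. Chance of a significant result.** Simulation with 20,000 trials per cell, n = 30 and four phases (no-map, map, no-map, map). The per-person contrast is (−0.5, 0.5, −0.5, 0.5), tested by a two-sided 5% one-sample t test as a stand-in for the mixed model. Phase-to-phase wear SD is 0.5 h, base 10 h, with no change in the underlying rate. The columns are the within-person phase-to-phase CV of the rate.

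| Scenario | Measure | 10% | 15% | 20% | 30% |
|---|---|---|---|---|---|
| Equal wear | total, rate | about 5% | about 5% | about 5% | about 5% |
| +0.5 h, a = 1 | total | 64% | 38% | 24% | 13% |
| +0.5 h, a = 1 | rate | 5% | 5% | 5% | 5% |
| +0.5 h, a = 0.5 | total (mostly up) | 25% | 14% | 10% | 7% |
| +0.5 h, a = 0.5 | rate (mostly down) | 24% | 14% | 9% | 7% |
| +0.5 h, a = 0 | total | 5% | 5% | 5% | 5% |
| +0.5 h, a = 0 | rate (down) | 64% | 37% | 24% | 13% |

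On a 6 h base with a = 1, the total is significant in 91/70/50/28% of trials.

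**Step 4. Plausibility check by formula.** The contrast has the SD of one phase value, because 4 × 0.25 = 1. For a = 1 its relative SD is about √(CV² + 0.05²), where 0.05 = 0.5/10. The noncentrality is 0.05 × √30 / SD. At CV 10% this is 0.274/0.112 = 2.45, and at CV 30% it is 0.274/0.304 = 0.90. Against a critical value of 2.045, these fit the 64% and 13% above.

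**Step 5. Precision of a wear comparison.** The 95% CI half-width is 2.045 × SD/√30: 0.19 h for SD 0.5 h, and 0.37 h for SD 1 h. A true shift of 0.25 h is significant in only 76% and 25% of trials respectively, so a non-significant wear test does not show equal wear.

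**The case against.** **The total is a proper estimand.** Hypotheses 1 and 2 are worded as counts. If the map leads people to sit longer and so to move more in total, saying that the map increased movement is true of that total. This stands: the a = 1 figures above count such a rise as an error only when the question is movement per hour, or when the extra hours are device wear unrelated to the map.

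**Wear time is not ignored.** Non-wear seconds are excluded from the VM sum, participants invert the device when it is off, and logs are checked against raw data in doubtful cases. This also stands, so a reader who infers that the plan makes no use of wear time goes too far. Excluding non-wear removes spurious signal, but it does not equalise exposure or show whether exposure differed by condition.

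**The design is within-subject, with repeated reversal.** Stable differences between people cancel. Differences in hours that follow the map on/off schedule do not.

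**Differential wear is hypothetical.** Correct. The same people, device and wear instruction apply in all four weeks. The spread from 5% to 64% for one 0.5 h shift says nothing about which value applies to this trial.

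**This is small, minimal-risk work.** The template waives power analyses and endpoints, and the stated purpose is exploratory. That argues for a light remedy. It does not exempt a planned causal statement from a basic exposure check.

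**Conclusion.** The gap is real and visible in the text: both movement outcomes carry the length of the observed day, and nothing in the analysis plan adjusts for it or displays it by condition. Its consequence is conditional on hours differing between map and no-map weeks. With equal hours, total and rate both hold about 5%. With 0.5 h/day more in map weeks on an assumed 10 h, the total is significant in 13% to 64% of trials if the added time is as active as the rest, and in about 5% if it is inactive. These ranges rest on assumed hours, wear SD and rate variability.

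Two stronger readings are tempting and are not supported:
- *The totals are biased and the trial's conclusion invalid.* The documents contain no wear data and no evidence of differential wear, and the total matches the hypotheses.
- *A per-hour rate should replace the total.* The rate is misled as often as the total when the added hours are quiet (64/37/24/13%, downward). It also leaves out any map effect on chair time.

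This should be fixed, because the remedy is cheap and the causal wording depends on it. It does not threaten the design.

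**What to change.** 1. Report device wear hours and logged chair hours by phase, each with the map versus no-map difference and its 95% CI. Read the interval rather than a significance test.
2. Keep the daily total as the primary measure. Pre-specify an analysis of VM and weight shifts per wear hour beside it, using all wear hours, active plus inactive. For counts, a log wear-hours offset is an alternative.
3. Where total and rate disagree, or wear differs between phases, word the conclusion in the Data Analysis Plan to say whether the increase is in total movement or in movement per hour.
4. Reword the per-second sentence in item 1a so that it agrees with the daily sum in the Data Analysis Plan.

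A formal rule that permits the causal statement only if total and rate agree, or if the wear difference lies within a margin, is not advised. With a 0.5 h margin and a 0.25 h shift (a = 1), the margin route lets through upward false claims in 13/8/6/5% of trials at rate CV 10/15/20/30%. If 0.5 h of added time is 1.5 times as active as the rest, total and rate both rise significantly in about 23/12/9/6%.

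Cost: a few lines of post-processing, one table, one extra model per outcome and a few sentences. No new data are needed, since wear time is already derived and the chair log already kept. The downside is a little more analysis, and a rate that falls when added hours are quiet, so total, rate and hours must be read together.
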